Estimated date first patient enrolled: Q3 2018

Estimated date last patient completed: Q3 2022

Phase of development:

3

Objectives:

Primary Objective:

To confirm the efficacy of glepaglutide in reducing parenteral support (PS) volume in SBS patients

Secondary Objectives:

- To evaluate the efficacy of glepaglutide on other efficacy endpoints in patients with SBS
- To evaluate the safety and tolerability of glepaglutide in patients with SBS

Methodology:

This is a multicenter, placebo-controlled, randomized, parallel-group, double-blind, fixed dose, Phase 3 trial to demonstrate the superiority of once weekly and twice weekly subcutaneous (SC) injections of 10 mg glepaglutide versus placebo in stable SBS patients.

After providing informed consent and initial confirmation of eligibility during the 2-week Screening period, patients will enter a PS Optimization and Stabilization Phase before baseline measurements are performed. An individual drinking menu will be defined by the patient and the Investigator during the Screening period and until the end of the Optimization Phase. All patients will be equipped with an electronic diary (eDiary) for recording of trial relevant data/information.

Unless otherwise specified, baseline is defined as Day 1, prior to first dosing of trial product.

Optimization Phase

During the Optimization Phase, the Investigator may change the PS volume and content if the patient is considered unstable or not optimized. Any changes in PS volume or content will be administered according to institutional standard practice. The effect of any PS optimizations must be investigated after 2 weeks. Prior to an Optimization Phase visit, the patient must measure his/her urine over 48 hours, while adhering to the pre-defined drinking menu, and report the urine volume and oral fluid intake in the eDiary. PS optimization consist of 2 rounds, which limits the Optimization Phase to a maximum duration of 4 weeks (\pm 4 days). If optimization cannot be shown during the 4-week period, a second Optimization Phase of up to 4 weeks (\pm 4 days) is allowed. The last Optimization Phase visit can be combined with the first visit in the Stabilization period if the patient is considered optimized.

Stabilization Phase

The Stabilization Phase has a minimum duration of 2 weeks and a maximum duration of 4 weeks (\pm 4 days). The last visit of the Optimization Phase can also be the first visit of the Stabilization Phase. Prior to the Stabilization Phase visit, the patient must measure his/her urine over 48 hours, while adhering to the pre-defined drinking menu, and report the urine volume and oral fluid intake in the eDiary. Patients will be evaluated every 2 weeks during the Stabilization Phase and will need to fulfill the pre-specified stability criteria before the patient can be randomized. If stability cannot be shown during the 4-week period due to unforeseen events such as infections, illness or similar, a second Stabilization Phase of up to 4 weeks (\pm 4 days) is allowed.

A patient will be considered stable if all the following criteria are met:

- Actual PS usage (volume and content) matches prescribed PS ($\pm 10\%$ deviation in volume is acceptable) and
- 48-hour urine volumes at 2 consecutive visits within a 2-week interval (± 4 days, i.e., visits should be 10 to 18 days apart) are similar (a maximum of $\pm 25\%$ deviation is acceptable), while the oral fluid intake is constant (the two 48-hour oral intakes differ less than 10%) and maximum 3.5 L per day and
- Urine volume is on average ≥ 1 L and ≤ 2.5 L per day.

The Investigator and Medical Monitor must both agree and approve that the patient has met the criteria to be considered stable after completing the Stabilization Phase.

The baseline PS volume (L/week) will be defined as the actual PS volume received during the 7-day period prior to Visit 1 (Day 1). The baseline daily urine volume (L per day) will be defined as the average of the last two 48-hour urine volume measures from the Stabilization Phase. For scheduling of the 48-hour measurement periods throughout the trial, see [Table 4](#).

Main trial period:

Visit 1 is done within 2 weeks after the last Stabilization Phase visit. All eligible patients who complete the Optimization and Stabilization Phases will be randomized in a 1:1:1 manner to receive either: a) glepaglutide 10 mg twice weekly, b) glepaglutide 10 mg once weekly and placebo once weekly, or c) placebo SC twice weekly for the following 24 weeks.

During the 24-week Treatment Phase, PS need will be evaluated by 48-hour balance periods involving urine measurements and during which patients will be required to keep to an individually pre-defined drinking menu (timing, volume, and content) and document this in the eDiary.

The actual volume of PS will be recorded on an ongoing basis in electronic diaries (eDiaries) by the patients. The Investigator will record the type, content, and volume of the PS being used. Once trial drug treatment is initiated, PS volume can be adjusted at trial visits (at Weeks 1, 2, 4, 8, 12, 16, 20, and 24) if the criteria for adjustment are met and according to a predefined algorithm.

Algorithm for PS volume reduction:

IF: daily average urine volume of the current visit is at least 10% higher than baseline urine volume.

THEN: New PS volume (weekly) = Current PS volume (weekly) – 7 x absolute increase in daily urine volume from baseline

The Investigator may arrange unscheduled visits (preceded by a 48-hour balance period) if he or she considers the visits to be needed based on medical judgement to assess PS volume needs.

It is acknowledged that intake of oral liquids and PS might have to be changed between scheduled visits to avoid edema, especially if treatment is effective. In such cases changes to the PS is at the discretion of the Investigator and the reason needs to be documented in the eCRF.

Any changes to the content of PS are left to the discretion of the Investigator and the reason is documented in the eCRF.

After completing the Treatment Phase, all patients (patients in all 3 treatment groups) will be eligible to enter an Extension Trial and receive glepaglutide. In addition, patients who were dosed but discontinued from trial treatment due to reasons other than an unacceptable adverse event (AE) related to the trial product or withdrawal of consent may be invited to enter the Extension Trial when completing the 24-week Treatment Phase schedule. For patients not entering the Extension Trial, a Follow-up Visit will be conducted 4 weeks after completion of the Treatment Phase.

Target Patient Population:

Key patient inclusion criteria include:

- Diagnosis of SBS defined as remaining small bowel in continuity of estimated less than 200 cm [equal to 79 inches] with the latest intestinal resection being at least 6 months prior to Screening and where the patient is considered stable with regard to PS needs. No restorative surgery planned in the trial period.
- PS requirement of at least 3 days per week as assessed prior to Screening and at the end of the Optimization and Stabilization Phases.
- Willing to adhere to an individual pre-defined drinking menu and urine measurement during the 48-hour measuring intervals.
- Age \geq 18 years and \leq 90 years at Screening.
- At randomization: Maintains a stable PS volume for at least 2 weeks prior to randomization.

Trial products, dosage and mode of administration:

Glepaglutide: Provided in single-use vials containing 1 mL (an extractable volume of 0.5 mL) of a clear, essentially colorless solution for injection, containing 20 mg/mL glepaglutide. Patients randomized to active treatment will inject 10 mg (0.5 mL) glepaglutide either a) twice weekly or b) once weekly and placebo once weekly.

Reference therapy: Placebo is provided in single-use vials containing 1 mL (an extractable volume of 0.5 mL) of clear, essentially colorless solution for injection. Patients randomized to placebo treatment will inject (0.5 mL) placebo solution twice weekly.

Intervention groups and duration:

Duration of treatment is 24 weeks across treatment groups.

- Glepaglutide twice weekly: 10 mg glepaglutide on Day 1 and on Day 4 or 5 (same days of the week every week)
- Glepaglutide once weekly: 10 mg glepaglutide or placebo on Days 1 and on Day 4 or 5 (same days of the week every week)
- Placebo: placebo on Day 1 and on Day 4 or 5 (same days of the week every week)

Endpoints:Primary Endpoint:

Reduction in weekly PS volume from baseline to Week 24

Key secondary endpoints:

- Clinical response, defined as achieving at least 20% reduction in weekly PS volume from baseline to both Weeks 20 and 24
- Reduction in days on PS \geq 1 day/week from baseline to Week 24
- Reduction in weekly PS volume from baseline to Week 12
- Reduction in weekly PS volume of 100% (weaned off) at Week 24

Secondary efficacy endpoints:

- Reduction of at least 20% in PS volume from baseline to both Weeks 12 and 24
- Change in fluid composite effect (FCE) from baseline to Week 24
- Reduction in calculated energy content of parenteral macronutrients from baseline to Week 24
- Reduction in number of days on PS per week from baseline to Week 24
- Reduction of at least 40% in PS volume from baseline to both Weeks 20 and 24
- PGIC improvement at Weeks 4, 12, 20, and 24

- Change in weight from baseline to Week 24

Other efficacy endpoints:

- Reduction in days on PS \geq 2 days/week from baseline to Week 24
- Reduction in days on PS \geq 3 days/week from baseline to Week 24
- Reduction in duration of PS infusions per week from baseline
- Concentration trough levels of glepaglutide and metabolites
- Change in plasma citrulline level from baseline to Week 24
- Change in weekly need for parenteral micronutrients (sodium, potassium, magnesium and calcium) from baseline to Week 24
- Change in patient-reported outcomes (SBS-I and EQ-5D-5L) from baseline to Week 24
 - Reduction in bowel movements or stoma bag emptying from baseline to Week 24 Safety endpoints:
- Incidence and types of AEs and serious adverse events (SAEs)
- Change in clinical evaluations:
 - Vital signs
 - Electrocardiogram (ECG)
 - Change in safety laboratory assessments:
 - Hematology
 - Biochemistry
 - Urinalysis
 - Standard bone markers
 - Immunogenicity

Statistical methodology:

Inferential statistical analyses of the primary and secondary efficacy endpoints will be performed. All comparisons will be between each glepaglutide treatment group and placebo. No statistical interim analysis is planned.

Analysis Sets

- The Full Analysis Set (FAS) will consist of all randomized patients, who received at least one dose of trial drug (glepaglutide or placebo). All efficacy analyses will be based on the FAS.
- The Per-protocol Analysis Set will consist of all FAS patients who do not experience any major protocol deviations. Final judgments on exclusion from the Per-protocol Analysis Set will be made prior to database lock. The Per-protocol Analysis Set will be used for supplementary analyses of the primary and key secondary efficacy endpoints.
- The Safety Analysis Set will consist of all randomized patients, who received at least 1 dose of trial drug (glepaglutide or placebo). This is the same definition as for the FAS, but the two can deviate in special circumstances. All safety analyses will be based on the Safety Analysis Set.

Analysis of primary and key secondary endpoints

The primary analysis of the primary efficacy endpoint uses a restricted maximum likelihood-based repeated-measures approach to compare treatment groups with respect to the mean change from baseline in weekly PS volume at Week 24. The model will use weekly PS volume assessments at Week 1, 2, 4, 8, 12, 16, 20, and 24, and will include the covariates for treatment group, baseline weekly PS volume, visit (categorical variable), stratification factor (weekly PS volume requirements <12 L/week versus >12 L/week), and visit-by-treatment group interaction. Missing values will be

imputed using multiple imputation methods. For the primary analysis, a Copy Reference approach is used with placebo treatment as reference, while for sensitivity analyses, a Jump to Reference and a Copy Incremental from Reference approaches will be applied. As a supplementary analysis, the analysis will be repeated using the Per-protocol Analysis Set.

The 4 key secondary efficacy endpoints will be analyzed to assess the treatment effect using the FAS. Continuous endpoints will be analyzed in a similar manner as the primary efficacy endpoint. The binary endpoint of clinical response will be tested using the Cochran-Mantel-Haenszel test with stratification on the randomization stratification factor (weekly PS volume requirements <12 L/week versus >12 L/week). As a supplementary analysis, the 4 key secondary endpoints analyses will be repeated using the Per-protocol Analysis Set.

Gatekeeping Procedure

A parallel gatekeeping testing procedure will be used to protect the overall type I error rate of α testing the primary endpoint together with the key secondary endpoints between each glepaglutide treatment group versus placebo. The twice weekly treatment group and once weekly treatment group comparisons to placebo will be tested by splitting α into 2 $\alpha/2$ comparisons.

Secondary endpoints

The secondary efficacy endpoints will be analyzed to assess the treatment effect using the FAS. The tests will be non-hierarchical and type I error will not be adjusted for multiple testing. The other efficacy endpoints will be summarized to assess the treatment effect using the FAS. Only descriptive statistics will be presented for these other efficacy endpoints and no inferential statistics will be performed.

Safety Analysis

All safety analyses will be conducted using the Safety Analysis Set. No inferential tests of safety data will be performed. Descriptive summaries of safety data will be presented. Adverse events (treatment-emergent unless otherwise specified) will be presented by system organ class (SOC) and preferred term (PT) for each treatment group.

Discontinuations and Data Handling Rules

The analysis for the primary efficacy endpoint as well as for the continuous key secondary efficacy endpoints will handle missing values using a CR-imputed data set generated from the multiple imputation approach described for the primary efficacy endpoint. For all responder analyses, patients who discontinue for any reason will be considered as non-responders from the time of discontinuation onwards. No pooling of sites is planned for the efficacy analyses.

Number of patients (planned):

Approximately 108 patients are planned to be randomized into the trial 1:1:1.

[figure not shown]

Figure 1: Trial Design

Table 1: Schedule of Assessments

Phase	Screening	Run in: PS optimization phase	Run-in: PS stabilization phase	Treatment phase								EOT	FU ¹⁹	
				D1 ¹⁸	D3	D8	D15	D29	D57	D85	D113	D141		
Visit day or week	up to 14 d prior to Op1	Duration: 2 to 4 weeks \pm 4d*	Duration: 2 to 4 weeks \pm 4d*	\pm 1	\pm 2 (W1)	\pm 3 (W2)	\pm 5 (W4)	\pm 5 (W8)	\pm 5 (W12)	\pm 5 (W16)	\pm 7 (W20)	\pm 7 (W24)	D197 \pm 7 (W28)	
Visit #	Sc	Op1, Op2 etc.	St1, St2 etc.	V1	V2	V3	V4	V5	V6	V7	V8	V9	V10	FU
Visit type (site, phone)	S	S	S	S	P	S	S	S	S	S	S	S	S	S
Informed consent	X ¹													
Inclusion/exclusion criteria	X			X										
Demographics (age, gender, race and ethnicity [if allowed in the participating country])														
Medical history and concomitant illness	X ²													
SBS characteristics	X													
PS regimen (day, volume, and content) ³	X	X	X	X	X	X	X	X	X	X	X	X	X	
Definition of individual drinking menu (volume, content & timing) ⁴	X	X	X	X	X	X	X	X	X	X	X	X	X	
Body weight/height (height at Sc only) ⁵	X	X	X	X	X	X	X	X	X	X	X	X	X	
Concomitant medications/procedures	X	X	X	X	X	X	X	X	X	X	X	X	X	
ECG	X			X										X
Vital signs (heart rate, blood pressure, body temp)	X	X	X	X	X	X	X	X	X	X	X	X	X	
Adverse Events		X	X	X	X	X	X	X	X	X	X	X	X	
Physical examination (Full PE at Sc; SBS symptom-driven at all other visits)		X (full)		X	X	X	X	X	X	X	X	X	X	
Colonoscopy	X ⁶													
Laboratory														
Urine sample ⁷	X	X	X	X	X	X	X	X	X	X	X	X	X	
Pregnancy test for females of childbearing potential only	X	X	X	X										X
Hematology and Biochemistry ^{8, 9, 10}	X	X	X	X										X
Citrulline ¹¹				X										X
PK ¹¹				X										X

Protocol ZP1848-17111. Final Version 10.10-27-Jan-2022
Glepaglutide SBS

Abbreviations: d=day; FU=Follow-up; Op=Optimization Phase visit; SBS=short bowel syndrome; Sc=Screening visit; St=Stabilization Phase visit; V=visit; W=week

* If optimization/stabilization cannot be shown during the 4-week period, a second Optimization/Stabilization Phase of up to 4 weeks (± 4 days) is allowed.

** In case the patient is considered stable at the last two St Visits, it is not needed to conduct another 48-hour period prior to Visit 1.

1. Informed consent must be obtained before any trial related assessments incl. the start of the 48-hour oral fluid intake and urine volume measurement. Informed consent may be obtained prior to the Screening Visit.
2. Including detailed information on whether the patient has a history of encephalopathy, ascites, cholestasis, steatosis, and/or cirrhosis. If yes, the outcome / histopathologic diagnosis and date of histopathologic diagnosis is reported. Any history of drug/alcohol abuse is reported. Information on smoking and current use of alcohol will be reported.
3. PS regimen will be based on information from the eDiary.
4. Define 24-hour drinking menu, which will be repeated twice during the 48 hour balance periods. It can be adjusted until the end of the Optimization Phase. After this, it may not be changed. Provide information and instructions to patients for documentation in eDiary.
5. Patients are encouraged to measure their body weight at home weekly to detect fluid retention early. If the weight changes, patients should call the trial site for guidance.
6. For patients with remnant colon, colonoscopy should be performed and evaluated before start of Optimization Phase. Colonoscopies performed as part of routine clinical practice (and prior to provision of informed consent) up to 6 months prior to Screening (Sc) are acceptable. In case a remnant colon is not connected to the passage of foods and thereby dormant, a computerized tomography (CT) scan or magnetic resonance imaging (MRI) (if standard of care at site) will suffice at the discretion of the Investigator to document the absence of concerns regarding malignancy.
7. Urinalysis: Blood, glucose, leukocytes, pH, osmolarity, protein, sodium, and potassium.
8. Hematology: Hemoglobin, hematocrit, red blood cell (RBC) count, white blood cell (WBC) count with differential, and platelet count. Biochemistry: Sodium, potassium, chloride, bicarbonate, blood urea nitrogen, creatinine, estimated CLcr, glucose, calcium, phosphorous, alkaline phosphatase, alanine aminotransferase (ALT), aspartate aminotransferase (AST), international normalized ratio (INR), gamma-glutamyl transferase (GGT), lactic dehydrogenase, conjugated bilirubin, total protein, albumin, amylase, uric acid, C-reactive protein (CRP). In case of suspected liver injury based on increased ALT, AST, alkaline phosphatase, or total bilirubin, the tests should be repeated at 48-72 hours for evaluation of the event course/confirmation.
9. In addition, cholesterol and triglycerides will be measured orally fasting at visits 1 (Day 1) and Visit 10 (Day 169/Week 24).
10. In addition, magnesium and zinc will be measured at visits 1 (Day 1), 7 (Day 85/Week 12) and 10 (Day 169/Week 24).
11. Blood draws for PK, ADA, and citrulline sampling must be done prior to dosing, if dosing occurs on the day of the visit. In case of treatment discontinuation, the patient will be asked to come for ADA sampling at EOT (End of Treatment) as well as approximately four weeks after treatment discontinuation.
12. Bone markers include: 25OH vitamin D, parathyroid hormone (PTH), thyroid stimulating hormone (TSH; thyrotropin), P-CTX (collagen I, C-terminal telopeptide-fragments), and P-PINP (Pro-collagen, N-terminal pro-peptide).
13. Questionnaires must be completed at site visits prior to any other trial related assessment. It is recommended that the PGC is completed first, followed by the SBS-I, then the EQ-5D-5L. The SBS-I and EQ-5D-5L are to be completed once during PS optimization phase, at the start of and after the stabilization phase, and all PROs are to be completed during treatment as indicated in the Schedule of Assessments. The exit interviews (Danish, French, German, UK and US sites only) will be conducted no longer than 7 days after EOT visit.
14. Remind patient of the next dosing day.
15. Train the patient to self-inject.
16. Patient should be instructed to return all used vials on an ongoing basis.
17. Treatment compliance should be discussed with the patient to ensure that the medication is being taken correctly and that a new vial is used for each injection.

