11.3.3 Weight and Height

Body weight (kg or lb) will be measured at Screening, during the Optimization and Stabilization Phases, and at every trial visit (except Visit 2-phone assessment). During weight measurements patients should wear light clothing and no shoes. Stoma bags should be emptied prior to the measurement. At Screening Visit height (cm or inches) will be measured and the patient's body mass index (BMI) will be calculated.

Patients should be encouraged to measure their body weight at home weekly to detect potential signs of fluid retention early (before edema becomes readily visible). If the weight changes, patients should be instructed to call the trial site for guidance.

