Reduction of at least 30% in actual weekly PS volume from baseline to both Weeks 20 and 24

The difference in response in reduction of $\geq 30\%$ in PS volume from baseline to both Weeks 20 and 24 between each glepaglutide treatment group comparison to placebo will be tested using the CMH test adjusted for the stratification factor will be analyzed in a similar manner as the clinical response endpoint (first key secondary endpoint).

Reduction in prescribed weekly PS volume of 100% (weaned off) at Week 24

The difference in response in prescribed weekly PS volume of 100% (weaned off) at Week 24 between each glepaglutide treatment group comparison to placebo will be tested using the CMH test adjusted for the stratification factor will be analyzed in a similar manner as the weaned off endpoint based on actual PS volume (fourth key secondary endpoint).

PGIC improvement at weeks 4, 12, 20, and 24

PGIC improvement is defined as responding "Very Much Improved" or "Much Improved" on a 7-point Likert Scale for each of the weeks 4, 12, 20, and 24. Improvement between each glepaglutide treatment regimen compared to placebo will be tested by week, using the CMH test adjusted for the stratification factor. In similar fashion, improvement between each glepaglutide treatment regimen versus placebo will be tested using collapsed categories of Improvement, No Change, and Worsening, where Improvement is defined as a response of "Very Much Improved" or "Much Improved" or "Minimally Improved", and No Change is defined as the response of "No Change", and Worsening is defined as a response of "Minimally Worse" or "Much Worse" or "Very Much Worse". Improvement using collapsed 25 August 2022 Confidential Page 24 of 65

categories between each glepaglutide treatment regimen compared to placebo will tested by week using a Mantel-Haenszel chi-squared test for ordered categories. No imputation for missing values will be performed.

Change in weight from baseline to Week 24

The change in body weight (kg) from baseline to Week 24 will be presented descriptively by baseline BMI subgroup. Descriptive statistics will include the number of non-missing observations, mean, SD, median, minimum, and maximum values. A shift table by BMI subgroup from baseline to Week 24 will be presented. The BMI subgroups are defined as: <18.5 kg/m2, \geq 18.5 to <25 kg/m2, \geq 25 to <30 kg/m2 and \geq 30 kg/m2.

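### Change in body weight is a secondary efficacy endpoint, but no whole-FAS comparison with placebo is pre-specified for it, contrary to the protocol synopsis

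*Protocol*

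**What the plan says.** **General statements.** The synopsis (Endpoints) and protocol 6.3.3 place "Change in weight from baseline to Week 24" among the secondary efficacy endpoints. The synopsis (Statistical methodology) says: "Inferential statistical analyses of the primary and secondary efficacy endpoints will be performed. All comparisons will be between each glepaglutide treatment group and placebo". Its paragraph on secondary endpoints adds: "The secondary efficacy endpoints will be analyzed to assess the treatment effect using the FAS", and then: "The tests will be non-hierarchical and type I error will not be adjusted for multiple testing". The same paragraph assigns purely descriptive reporting to the 'other' efficacy endpoints, and weight is not one of those. Protocol 12.1 repeats the statement about inference but refers to the descriptions that follow it.

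**Endpoint-specific text.** Protocol 12.3.4 summarises weight change descriptively in two baseline BMI groups, with bands of percentage change and the proportions under, at and over normal weight. SAP 3.4 says: "The change in body weight (kg) from baseline to Week 24 will be presented descriptively by baseline BMI subgroup". It uses four BMI groups and adds a BMI shift table and a table of three percentage-change bands.

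**Data.** Protocol 11.3.3 says: "Body weight (kg or lb) will be measured at Screening, during the Optimization and Stabilization Phases, and at every trial visit", with only the Visit 2 phone contact excepted. The treatment phase therefore yields eight post-baseline weights per patient, at Weeks 1, 2, 4, 8, 12, 16, 20 and 24.

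**The concern.** The general text puts weight in a tier that is compared with placebo. The specific text gives it no model, test, between-arm difference or confidence interval. Both cannot describe the same plan.

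The trial reduces parenteral support, so readers will ask whether weight on each regimen moved differently from weight on placebo. Inclusion criterion 6 asks patients to be willing to hold weight within 5%, and protocol 11.3.3 uses home weighing to detect fluid retention. As planned, the reader gets Week 24 means within BMI groups and a count by bands. There is no overall contrast per regimen, no adjustment for baseline weight, no use of the intermediate weights and no stated handling of missing Week 24 values. Any between-arm figure quoted later would be post hoc.

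**Working it through.** The documents state no figure for this point, so the check is mainly textual.

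**1. Is a comparison for weight planned anywhere?** The endpoints in SAP 3.4 compare as follows.

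| Endpoint in SAP 3.4 | Comparison with placebo |
|---|---|
| At least 20% PS reduction, Weeks 12 and 24 | As first key secondary endpoint (CMH) |
| Parenteral energy content | MMRM |
| Number of PS days per week | MMRM |
| At least 40% and at least 30% PS reduction | CMH |
| Weaned off, prescribed volume | CMH |
| PGIC improvement | CMH, plus an ordered-category test |
| Prescribed weekly PS volume | Primary-endpoint method |
| Body weight | None |

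Some lower-tier endpoints get more. SAP 3.5 applies the confirmatory binary method to reductions of at least 2 and at least 3 PS days, and t-tests to SBS-I and the EQ-5D-5L index. Protocol 12.3.5 had made all of these descriptive.

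The safety sections do not fill the gap. Protocol 11.3.1 names weight as a safety parameter, but SAP 3.6 does not list it and SAP 7.4 covers only heart rate, blood pressure and temperature.

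**2. What could be recovered from the planned tables?** Protocol 12.1 provides summaries by treatment group. The four SAP BMI groups are exhaustive and do not overlap, and n, mean and SD are reported for each. With n_k and m_k the count and mean in BMI group k, an arm's overall mean change is

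m = Σ n_k m_k / Σ n_k,

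and the difference of two such means is a crude arm contrast. It would be unplanned, restricted to observed cases, and unadjusted for baseline weight or stratum.

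**3. Scale of precision (illustration).** Inputs: 108 patients, 36 per arm (protocol 7.1). Assumptions: no dropout, and an even spread over the four SAP BMI groups, so 108 / (4 × 3) = 9 per cell. The 95% half-width of an unadjusted difference, in units of the SD of weight change, is t(0.975; 2n − 2) × √(2/n):

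- Whole arms, n = 36: 1.994 × √(2/36) = 1.994 × 0.2357 = 0.47 SD.
- One BMI cell, n = 9: 2.120 × √(2/9) = 2.120 × 0.4714 = 1.00 SD.

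The ratio of standard errors is √(36/9) = 2. The documents give no SD for weight change, so these stay in SD units.

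**The case against.** The strongest reply is that specific text governs general text. Protocol 12.1 ties its statement about inference to what follows, and what follows in 12.3.4 is descriptive for weight. The SAP is the overriding analysis document and is descriptive too. Lead-in sentences are also loose: the one in SAP 3.4 says actual PS volume will be used in the analyses, which cannot apply to weight. This settles what will be run. It does not remove the contradiction with the synopsis, which states no exception and keeps descriptive-only reporting for another tier.

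Several stronger readings are tempting, and the documents do not support them:

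- **That the SAP dropped a promised comparison without saying so.** Protocol 12.3.4 was already descriptive, so SAP section 8 had no dropped weight comparison to record. It does record the new BMI groups and the shift table. It also records the one real loss of this kind, the replacement of the fluid composite effect model by graphs.
- **That no estimate of any kind could be obtained.** A crude difference can be rebuilt, as shown above.
- **That every weight table is split by BMI.** The percentage-change bands in SAP 3.4 are not described that way.
- **That weight is the plan's designated check of nutritional adequacy.** The documents do not say so. Weight also serves as a fluid-retention signal, and SAP 3.4 models parenteral energy.

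It is also fair to say that nobody plans within-cell arm differences. The 1.0 SD figure therefore shows what a reader comparing cells would face, not the precision of a planned analysis.

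**Conclusion.** The point holds in limited form. The synopsis conflicts with protocol 12.3.4, and SAP 3.4 inherits the conflict. A declared secondary efficacy endpoint is left without a pre-specified between-arm estimate, confidence interval or test in the FAS, alone among the endpoints in SAP 3.4. That finding rests on the text and needs no assumption.

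The precision figures, 0.47 SD against about 1.0 SD, are illustrative. They rest on 36 per arm, no dropout and an even 9 per BMI cell. A different BMI distribution would make some cells more precise and others less.

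Weight is outside the multiplicity-controlled family, so no confirmatory conclusion changes. The change is still worth making before unblinding, because the data are already scheduled and the model already exists.

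**What to change.** In SAP 3.4, add an MMRM of change in body weight (kg) in the whole FAS. Include treatment, visit, treatment-by-visit interaction, baseline weight and the randomisation stratum, and use all scheduled post-baseline treatment-phase weights. Report each regimen minus placebo at Week 24 with a 95% CI, unadjusted for multiplicity like the rest of the tier. State how missing weights are handled; protocol 12.3.4 offers a precedent in its MMRM without multiple imputation for parenteral energy. Keep the BMI-group, shift and band tables as descriptive support, and record the addition in SAP section 8.

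The cost is one paragraph and one more run of an existing model, with no new data. If the sponsor prefers to leave weight descriptive, the minimum is to say so explicitly in the synopsis, protocol 12.1 and SAP 3.4. That removes the contradiction but still leaves no planned comparison.
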